## 2. Secondary:

- Comparison of the results obtained on the Constant scale with a surgical historical cohort that were treated by shoulder prostheses for this same pathology.
- Complications arising from non-surgical treatment.

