## 10. Population under study and total number of patients

Number of patients: The cohort to study includes of 20 patients in which we have opted for non-surgical treatment. The historical cohort consists of 20 patients undergoing shoulder replacement.

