## 11. Study calendar

The start date of the study will be the 1st and 2nd quarter of 2017.

- Recruitment of patients: 12 months
- Follow-up period (1 year per patient): 22-24 months
- Data analysis: 3 and 12 months.

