## Statistical analysis

1 Sample size: Accepting an alpha risk of 5% and a beta risk of 20% in a bilateral contrast, 20 patients are required in each group to detect a difference equal to or greater than 13 units in the ASES scale score. The common standard deviation is assumed to be 15.

2 Statistical analysis: Qualitative variables shall be expressed as absolute frequencies and percentages while quantitative variables shall be presented as typical means and deviations or as medians and inter-quarterlic range depending on their normality.

Initially, the comparability of both groups will be studied to check the homogeneity of the randomization groups. Comparisons of the ASES scale and all other numeric variables between two groups will be made with student's t-test of independent measurements or Mann-Whitney test, as deemed appropriate. For repeated measurements at 3 and 12 months, the Student's t of repeated measurements or Wilcoxon test shall be used. To study the association of categorical variables, the Pearson ji-square or Fisher exact test will be used.

Differences whose p-value associated with the contrast test is less than or equal to 0.05 shall be considered significant. Data collection will be recorded in Excel database which will then be exported and analyzed in the SPSS 18 statistical program.

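### The comparison with surgery is declared on Constant alone but sized on ASES and tested on every numeric variable at an unadjusted 0.05, and no scale or visit is named as decisive

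*Combined protocol and SAP*

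**What the plan says.** Four places bear on the comparison between the sling cohort and the historical arthroplasty cohort.

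- **Section 8, Valuation variables, Secondary.** One scale is declared, with no visit: "Comparison of the results obtained on the Constant scale with a surgical historical cohort that were treated by shoulder prostheses". The matching secondary objective in section 6 speaks only of results in general, so it does not narrow or widen this.
- **Statistical analysis, item 1 (sample size).** The calculation is for two groups: "Accepting an alpha risk of 5% and a beta risk of 20% in a bilateral contrast, 20 patients are required in each group". It uses a different scale from section 8, since the stated aim is "to detect a difference equal to or greater than 13 units in the ASES scale score". On variability the plan adds: "The common standard deviation is assumed to be 15".
- **Statistical analysis, item 2.** The testing sentence covers more than either scale: "Comparisons of the ASES scale and all other numeric variables between two groups will be made with student's t-test of independent measurements", with Mann-Whitney as the alternative. The decision rule is general: "Differences whose p-value associated with the contrast test is less than or equal to 0.05 shall be considered significant".
- **Timing.** The shoulder consultation schedule has ASES, Constant, DASH and VAS at 3 months and again at 12 months. Section 11 adds "Data analysis: 3 and 12 months". Within the Statistical analysis section, the two visits are mentioned only for the paired (within-patient) tests.

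The documents give no order of testing, split of alpha, decisive visit or exploratory label for these comparisons.

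**The concern.** The declared comparison, the sized comparison and the tested comparisons are three different things: Constant, ASES, and all numeric variables. If Constant and ASES disagree, or 3 months and 12 months disagree, the plan gives no way to tell which result answers the objective. Each test that reaches 0.05 may be reported as significant, so the more scales and visits are compared, the more likely it is that at least one difference appears by chance.

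This comparison is labelled secondary, but it carries much of the study's purpose. The Justification section rests on whether surgical results are better than conservative ones, and the only sample-size calculation is for a difference between two groups. A chance finding on one scale at one visit could therefore shape the trial's main message about sling versus surgery.

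**Working it through.** **Step 1. The plan's own figure.** Inputs from Statistical analysis, item 1: difference 13 on ASES, SD 15, two-sided alpha 0.05, power 80%.

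n per group = 2 × [15 × (1.960 + 0.842) / 13]² = 20.9, which rounds up to 21.

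The plan states 20. That is within rounding and is not in dispute. With 20 per group, power is 78.3% by the normal approximation and 76.1% by the t-test. Section 10 gives 20 patients in each cohort, so the comparison is 20 versus 20.

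**Step 2. How many between-group tests?** The documents do not fix this, so several counts are carried forward.

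- *Eight*: four scales at two visits. This is inferred from the consultation schedule and the calendar line. The between-group sentence itself names no visit.
- *Four*: four scales at one visit.
- *Two*: Constant and ASES at one visit, or Constant at both visits.
- *One*: a single scale at a single named visit. The plan does not currently define this.

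Eight is not a firm maximum, because the reference to all other numeric variables is open-ended. It may also be too many, because the documents do not say which scales or visits exist for the historical cohort.

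**Step 3. Chance of at least one false positive, independent tests.** The formula is 1 − (1 − 0.05)^k.

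- k = 2: 1 − 0.95² = 9.75%
- k = 4: 1 − 0.95⁴ = 18.5%
- k = 8: 1 − 0.95⁸ = 33.7%

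**Step 4. The same chance with correlated scores.** The scales measure overlapping things in the same patients, so independence overstates the rate. The documents give no correlations, so the values below are assumptions. Trials of 20 versus 20 were simulated with no true difference on any scale, using two-sided t-tests at 0.05.

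| Comparisons | Assumed correlation | At least one p ≤ 0.05 |
|---|---|---|
| 8 (4 scales, 2 visits) | none | 33.7% |
| 8 | scales 0.5, visits 0.5 | 27.3% |
| 8 | 0.5 between every pair | 25.4% |
| 8 | scales 0.7, visits 0.5 | 22.9% |
| 8 | scales 0.9, visits 0.8 | 14.2% |
| 4 (one visit) | none | 18.5% |
| 4 | scales 0.5 | 15.7% |
| 4 | scales 0.9 | 9.6% |
| 2 (Constant and ASES, one visit) | none to 0.9 | 9.75% to 7.0% |
| 2 (Constant, both visits) | none to 0.8 | 9.75% to 7.8% |
| 1 (one scale, one named visit) | not applicable | 5% |

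**Step 5. What a fixed order would cost.** Suppose Constant is tested first and ASES only if Constant is significant. Assume both scales have the sized standardized effect, 13/15 = 0.87. ASES tested alone has 76% power. The chance that both are significant is 0.761 × 0.761 = 58% if the scales are uncorrelated, and by simulation about 63-64% at correlation 0.5 and 70-71% at 0.9. If the true effect on Constant is smaller, the chance is lower.

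**The case against.** The strongest reply has five parts.

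- **The testing sentence may choose methods, not endpoints.** It can be read as saying which test suits numeric data, while section 8 says which comparison counts. This is a fair reading, but it does not explain why ASES is named there and used for the sample size while Constant is the declared variable. The mismatch stands.
- **Eight tests are not stated.** This is correct. The 3- and 12-month visits are attached only to the paired tests, the visit schedule is for the prospective patients, and the calendar line specifies no between-group test. Eight is one scenario. The rate still exceeds 5% with any second scale or visit.
- **A reader might infer a single figure: that the false-positive chance is about a quarter instead of 5%.** The documents do not support that. About 25-27% needs eight tests and correlations near 0.5, and the documents supply neither. The 5% comparator also presumes a single named visit, and section 8 names none; Constant at both visits already gives about 8-10%.
- **Secondary comparisons in a small, open, non-randomized study need no formal alpha control, and no rule says that one significant scale proves a treatment difference.** Both points are fair. The sole formal hypothesis, in section 9, concerns improvement with non-surgical treatment, and the significance rule applies to individual differences. An exploratory label would be enough, but the plan has none and applies one significance rule throughout.
- **Bias from historical controls matters more than multiplicity.** It may, and no alpha rule removes it. It is a separate problem and does not settle which scale or visit answers the question.

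**Conclusion.** The point holds as an inconsistency with a measurable consequence. The comparison with surgery is declared on Constant, sized on ASES and tested on all numeric variables, with no decisive scale or visit and an unadjusted threshold. On any reading with more than one scale or visit, the chance of at least one false-positive difference exceeds 5%. The excess is modest for two tests and larger for four or eight, and its exact size cannot be fixed from the documents because it depends on an unstated test count and unstated correlations. All the rates assume no true difference and otherwise comparable groups, so they measure chance error only.

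The finding concerns the between-group comparison and does not touch the main hypothesis in section 9. It should be corrected: the change is cheap and affects what the trial can claim about sling versus surgery.

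**What to change.** Before the data are analysed, reconcile section 8 (Secondary) with the Statistical analysis section by naming one scale at one visit as the single between-group test, two-sided at 5%. Either choice of scale is workable:

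- keep Constant, as section 8 declares, and state that the sample size was calculated on ASES and that no power is stated for Constant; or
- change section 8 to ASES, the scale that was sized.

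Use 12 months, provided that visit exists in the historical data. Report all other between-group comparisons (other scales, other visit) as exploratory, with mean differences and 95% confidence intervals. For between-group claims, limit the 0.05 significance sentence to the named test.

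The cost is a few sentences, with no extra patients or data. The downside is that an isolated significant result on another scale or visit can no longer be claimed as a confirmed difference from surgery. If the sponsor prefers a fixed sequence, Constant then ASES, both can be claimed at 5% overall, but the chance of claiming ASES falls from about 76% to about 58-71%, assuming equal standardized effects on the two scales.

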### *2. Clinical trial title*

"Treatment of proximal humeral fractures with sling." Prospective, non-randomized and open study to evaluate the effectiveness of orthopedic treatment in the management of three and four-parts proximal humeral fractures according to Neer's classification.

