### *7. Design*

Unicentric, prospective, non-randomized, open clinical trial comparing the effectiveness of the orthopaedic treatment for three and four-parts proximal humeral fractures in a patient population over 75 years of age.

Two treatments for these fractures will be compared secondarily:

1. Shoulder arthroplasty
2. Conservative treatment with sling followed by physiotherapy.

Both options are accepted today for the management in this type of fractures. [1, 2]

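### The sling cohort is compared with historical arthroplasty controls by unadjusted tests only, with no plan for cohorts that differ

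*Combined protocol and SAP*

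**What the plan says.** The title describes the trial as a "Prospective, non-randomized and open study to evaluate the effectiveness of orthopedic treatment", and the Design and the Type of control and design sections repeat that there is no randomisation. Under Selection process, sling patients are enrolled after emergency care, while the surgical controls are taken from a previous trial. No rule for choosing or matching those controls is given. On numbers, "The historical cohort consists of 20 patients undergoing shoulder replacement", against 20 sling patients.

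The comparison is labelled secondary. Section 7 states that "Two treatments for these fractures will be compared secondarily", and the secondary variable in section 8 is "Comparison of the results obtained on the Constant scale with a surgical historical cohort". The Justification of the study nevertheless presents surgery versus conservative treatment as the open question. The sample size also rests on a two-group difference, although in ASES rather than Constant: "20 patients are required in each group to detect a difference equal to or greater than 13 units in the ASES scale score".

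For the analysis, the plan says: "Initially, the comparability of both groups will be studied to check the homogeneity of the randomization groups". Comparisons of numeric variables "between two groups will be made with student's t-test of independent measurements or Mann-Whitney test, as deemed appropriate", and categorical variables are handled by Pearson chi-square or Fisher's exact test. The decision rule is: "Differences whose p-value associated with the contrast test is less than or equal to 0.05 shall be considered significant".

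**The concern.** Without randomisation, an unadjusted difference between cohorts combines the treatment effect with any difference in the patients. Both cohorts may contain 3- and 4-part fractures (Inclusion criteria; Treatment description), so the mix can differ. Age can differ too: the description of the historical cohort gives the fracture type but no age limit of its own. Selection process also says that, in the centre's current practice, the choice between prosthesis and sling depends on clinical and radiological features and on the patient's decision. That is a reason not to assume the cohorts are alike.

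The planned comparability check names no variables, no threshold and no consequence, and it is worded for randomised groups that do not exist here. If the cohorts differ in a factor that affects the score, the nominal 5% error rate no longer holds, and a real difference running against the bias can be hidden.

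**Working it through.** **Inputs from the plan (Statistical analysis; section 10).** 20 per group, SD 15 (stated for ASES), target difference 13 points, two-sided alpha 0.05, power 0.80. All imbalances, correlations and score differences below are assumptions, because the documents give none.

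**The plan's own figure.** n per group = 2 × [15 × (1.960 + 0.842) / 13]² = 20.9, so 21 by the normal approximation and 22 by the noncentral t. The stated 20 is close (power 78.3% normal, 76.1% noncentral t). The sample-size arithmetic is not the problem, but it assumes an unbiased comparison.

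**Can a balance test protect the comparison?** If the check is done by significance test, the noncentrality for a 0.5 SD imbalance is 0.5 / √(2/20) = 1.58 on 38 degrees of freedom, which gives power of 34%. For a 30% versus 50% split in four-part fractures, exact power is 16% (Fisher) or 25% (uncorrected chi-square). A non-significant result therefore says little.

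**Unadjusted test, no true effect.** The standard error is 15 × √(2/20) = 4.74 points. A covariate that differs by 0.5 SD and correlates r with the score shifts the difference by r × 0.5 × 15 points. Noncentrality is shift / 4.74.

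| r | Shift (points) | Noncentrality | False-positive rate |
|---|---|---|---|
| 0.2 | 1.5 | 0.32 | 6.1% |
| 0.3 | 2.25 | 0.47 | 7.5% |
| 0.5 | 3.75 | 0.79 | 12.0% |

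For larger total shifts of 5, 7.5 and 10 points, all below the 13-point target, the same formula gives 17.7%, 33.8% and 53.8%.

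**Neer mix, 30% versus 50% four-part.** If 3- and 4-part scores differ by 5, 10 or 15 points, the shift is 0.20 times that, or 1, 2 or 3 points. Simulated false-positive rates are 5.6%, 7.0% and 8.5%, with SD 15 within fracture type. If 15 is instead the total SD, the last figure is about 9.5%.

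**Regression on cohort, covariate and Neer type** (40,000 simulated runs per case, simulation error 0.1 to 0.2 percentage points). In all six cases above (three covariate, three Neer mix) the adjusted rate is 4.9% to 5.1%. That follows by construction, because the measured factor is the only confounder.

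**Adding an unmeasured shift** (r = 0.3 case, measured shift +2.25):

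| Unmeasured shift | Total shift | Unadjusted rejection | Adjusted rejection |
|---|---|---|---|
| +3.75 | +6.00 | 23.6% | 12.0% |
| +2.25 | +4.50 | 15.4% | 7.6% |
| −2.25 | 0 | 4.9% | 7.2% |
| −3.75 | −1.50 | 6.2% | 11.8% |

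Adjustment removes the measured 2.25 points. It helps when the unmeasured bias runs the same way and hurts in the two cases where it runs the other way.

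**Precision.** With a 0.5 SD imbalance, the average 95% interval half-width is 9.54 points unadjusted. Adjusted, it is 10.14 at r = 0, 9.94 at r = 0.2, 9.67 at r = 0.3 and 8.78 at r = 0.5.

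**The case against.** The main objective and the hypotheses concern improvement under sling treatment, and the arthroplasty comparison is consistently secondary. The design is openly labelled non-randomised, and a comparability check precedes the tests. The plan does not say that this check is a significance test, so the low detection rates apply only on that reading. The sample size is in ASES while the declared comparison is on Constant, so the sizing lends the comparison limited weight, and SD 15 is not given for Constant. The illustrated error rates are modest in most measured-confounder cases and rest wholly on assumptions. Adjustment leaves calendar time and treatment selection untouched and can worsen the error. Nobody can tell from the documents whether the earlier trial recorded the needed covariates.

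Most of this stands, and it limits the point to a secondary comparison with illustrative magnitudes. It does not remove the gap. A check with no consequence protects nothing, however it is done, and the Justification section makes this comparison the reason for the study. The figures show the mechanism; the defect does not depend on them.

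**Conclusion.** The concern holds, and the plan should be changed. As written, any case-mix difference between the cohorts that affects the score is counted as treatment effect, and nothing in the protocol corrects for it or limits the interpretation.

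The size cannot be determined from the documents. Under the assumed measured imbalances, the 5% error rate becomes 5.6% to 12.0%. It would be higher with larger or additional unmeasured differences in the same direction. These figures assume 20 per group, an SD of 15 carried over from ASES, and no true effect. The reference to randomisation in the comparability sentence is only a wording error.

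**What to change.** In the Statistical analysis section:

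- Make the between-cohort estimate a linear regression of the 12-month score on cohort, age and Neer type (3 versus 4 parts), with a 95% confidence interval. Use Constant, as section 8 specifies, and ASES as well if the historical dataset holds it. Age and Neer type are the two patient characteristics in the inclusion criteria, and 12 months is the last scored visit.
- Before analysis, confirm that these variables are recorded for the historical cohort. If they are not, say so and present the unadjusted difference as descriptive.
- Keep the t or Mann-Whitney results as an unadjusted supplement.
- Describe balance with standardised differences instead of testing it.
- Report the result as an association and state that residual confounding remains.
- Refer to study cohorts where the text now refers to randomised groups.

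The cost is SAP wording, one regression per score in SPSS, and two degrees of freedom. If the covariates predict little, the interval widens: half-width from 9.5 to 9.9 points at r = 0.2, or to 10.1 at r = 0. Unmeasured differences, including calendar time, remain, and adjustment may then reduce or increase the error. No extra patients or visits are needed.
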